STUDY PROTOCOL AND STATISTICAL ANALYSIS PLAN

Full Title: Addressing Racial Disparities in Autism Diagnosis and Treatment: Translating Peer-to-Peer Support into a Clinical Setting

Institution: University of Maryland, Baltimore

NCT Identifier: NCT04313283

Unique Protocol ID: HP-00090447

Secondary ID: 1UL1TR003098

PI: [name]

Co-PI: [name]

Date Last Approved by Institutional Review Board: 09/01/2022 (original approval: 03/26/2020)

Justification, Objective, & Research Design

Specific Aims

Aim 1. Deliver Parents Taking Action to caregivers of Black children with developmental delays on a waitlist for an autism or developmental evaluation. Parent Leaders (parents of children 9+ years and older with autism) will deliver the program to 20 caregivers of waitlisted children (ages 8 and younger). We include children referred for autism or developmental concerns, as well as older children, due to concerns about late and/or inaccurate referrals of Black children.

Aim 2: Assess the feasibility, acceptability, and short-term outcomes of Parents Taking Action with a clinical sample. We will measure pre/post changes in child (challenging behaviors) and caregiver outcomes (parenting stress; depression; and family functioning, including social support); and evaluate intervention process measures (acceptability and fidelity). We hypothesize the intervention will be acceptable and feasible and improve child and caregiver outcomes.

Design

Phase 1: We will expand our advisory group to include Brown on the Spectrum (BOS) and SOM representatives and other relevant stakeholders. This group will advise us on local service needs and potential barriers and facilitators for implementation. We will continue to consult with this group throughout the research process.

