Phase 2: To address Aim 1, we will identify and train four additional Parent Leaders (parents of children ages 9 years or older with autism). SOM clinical staff will identify eligible children and their families as they are added to the waitlist. The clinical team will also accept referrals internally from UM providers. We will send a letter from the research team leaders to potential participants via email (if available) and mail. The letter will let potential participants know that a research team member will be calling them about the study. The letter will also provide the research team's contact information, along with more study information. If participants are interested in the study, the research team member will go through the informed consent and intake processes. The research team will match Parent Leaders with caregivers, and provide caregivers with case management for housing and other needs.

Phase 3: To achieve Aim 2, we will evaluate program outcomes. Intervention participants will complete measures at three time points. Additionally, the Parent Leaders will complete weekly fidelity checklists. At the end of the program, we will interview intervention participants and Parent Leaders (separately) about the program, in order to obtain in-depth qualitative data on intervention acceptability and feasibility. We hypothesize Parents Taking Action 1) will be acceptable and feasible; 2) will reduce problem child behaviors, parent stress and depression; and 4) will improve family functioning.

Phase 4: We will complete data analyses, prepare manuscripts and conference presentations for peer review, and draft external grant proposals.

Study Procedures

This protocol involves two groups of human subjects: Parent Leaders (caregivers of older children with autism who deliver the intervention) and intervention participants (caregivers of children on an autism or developmental evaluation waitlist). The procedures for these groups are described below.

Parent Leaders Procedures

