NOTE: As needed, we will complete meetings and intervention delivery remotely. We will use secure video conferencing software (e.g., Webex, available through UMB) which allows phone-in or video joining options. For data collection, we will send participants secure Qualtrics links (a survey software available at UMB) to complete surveys. We will conduct and record interviews using video conferencing software (e.g., Webex).

Duration of Participation

Parent Leaders will be required to participate in 30-32 hours of training of Parents Taking Action Program, led by research staff. The Parent Leaders will work one-on-one with intervention participants to deliver two six-week modules (12 weeks total). Each Parent Leaders will be matched with approximately 4-5 caregivers each. Given it is not necessary for intervention participants' sessions to run concurrently, it is possible that Parent Leaders will deliver the intervention to their assigned caregivers through April 2021. We aim to hold the Parent Leaders post-intervention interviews in April 2021. These interviews will last approximately 60 minutes.

Three-time points measures (pre, post-module 1, and post-module 2) will take approximately one hour each for participants to complete. Post-intervention interviews with research staff will last approximately 60 minutes. We will use the same questionnaires for the three time points.

As noted above, as needed, we will hold the Parent Leader Training and intervention virtually.

Sample Size and Data Analysis

A convenience sampling method is appropriate for testing the feasibility and acceptability of this pilot trial. We aim to recruit additional 4 Parent Leaders and 20 intervention participants for this study. We will recruit potential intervention participants through waitlists for developmental or autism evaluations. (Children, particularly toddlers, who ultimately receive an autism diagnosis are often referred initially for developmental concerns.) To be eligible, participants must be the primary caregiver of a child eight years old or younger; and, identify their child as Black or African American.

Quantitative Data Analyses

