Based on a power analysis ($\alpha = .05$; effect size = .3; main outcome: parenting stress), we project a sample of 20 families adjusted for 10% attrition. We will use Generalized Estimating Equations (GEE) to analyze changes over time in parenting stress, caregiver depression, child behavior, and family functioning. Since we have three time points of data collection, we will use a commonly used method in repeated measures design, complete case analysis, to validate intervention effects (Bell, Fiero, Horton, & Chiu-Hsieh, 2014). In our study, we will consider baseline and T1 data (following completion of Module 1) a complete set. Furthermore, we will follow the manuals of our measures for protocols for missing data at the item level. For those measures without such guidance, we will use the Markov chain Monte Carlo multiple imputation method to address item-level missing data.

Qualitative Data Analyses

We will digitally record interviews and create an initial codebook based on the semi-structured interview guides. We will then analyze audio transcripts in NVivo 11 and code using open and axial coding processes. Consistent with grounded theory method (Corbin & Strauss, 2008), we will consult field notes, quantitative data findings, and research and program staff as themes emerge. We will actively seek responses not fitting the dominant themes (disconfirmatory responses) in order to understand the diversity of informants' perspectives. [name] and her research team will consult with [name] on final codes and themes until we reach consensus.

Data Integration

To aid our interpretation of the data, we will compare our data findings by reporter (e.g., Parent Leader versus caregiver acceptability) as well as type (e.g., qualitative versus quantitative caregiver acceptability).

Surveys/Questionnaires

1. Pre-post survey including demographic questionnaire and service use form, Nisonger Child Behavior Rating Form, Autism Parenting Stress Index, Center for Epidemiological Studies-Depression, Family Outcomes Survey-Revised
2. Post-intervention Social Validity Questionnaire
3. Weekly Procedural Fidelity Checklist Self-Assessment for Promotora Home Visits
4. Post-intervention Interview Guides for Parent Leaders and Parent Leaders

Duration of Expected Completion

1. Pre-post survey: 1 hour
2. Social Validity Questionnaire: 5 minutes
3. Weekly Procedural Fidelity Checklist Self-Assessment for Promotora Home Visits: 5 minutes

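### GEE on 18–20 families is planned with no small-sample correction; with the usual robust z test, a nominal 5% two-sided test of change would run at about 7.1–7.4%

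*Combined protocol and SAP*

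**What the plan says.** The quantitative plan is one paragraph of the combined protocol and SAP, under Quantitative Data Analyses. It gives alpha .05 and "effect size = .3; main outcome: parenting stress", and then says "we project a sample of 20 families adjusted for 10% attrition". The method is stated in one sentence: "We will use Generalized Estimating Equations (GEE) to analyze changes over time in parenting stress, caregiver depression, child behavior, and family functioning".

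Only missing-data handling follows. The plan will use "complete case analysis, to validate intervention effects", and defines what counts as complete: "In our study, we will consider baseline and T1 data (following completion of Module 1) a complete set". Item-level gaps are handled by the instrument manuals or by multiple imputation.

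No section states the variance estimator, working correlation, reference distribution, sidedness, time contrast or any small-sample correction. No rule for declaring an effect from a p-value is written either.

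Inference on change is nevertheless intended. Specific Aims says "We hypothesize the intervention will be acceptable and feasible and improve child and caregiver outcomes", and Design, Phase 3 expects that the programme "will reduce problem child behaviors, parent stress and depression".

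**The concern.** Standard GEE inference is a large-sample method. Its robust variance and normal reference rely on many independent clusters, and here there are at most 20. With so few, the uncorrected sandwich variance is too small on average and the z reference ignores its sampling variability. Both make tests reject too often and intervals too narrow.

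The plan sets an alpha but does not say which test has it. Defensible ways of running the named method give different error rates, and the choice could be made after the data are seen. At stake is whether a change in parenting stress, depression, child behaviour or family functioning with a p-value a little under .05 is reported as an effect. Phase 4 carries these results into manuscripts and grant proposals.

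**Working it through.** **Inputs from the plan.** Alpha .05; 20 families; 10% attrition, so 20 × 0.9 = 18 completers; three time points; one group.

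**The plan's own figure.** The sample of 20 cannot be reproduced, because the power, the metric of the .3 effect size and the within-family correlation are not given. It is attainable under some assumptions. For example, a repeated-measures ANOVA with f = .3, three time points and an assumed correlation of .5 needs 20 for 80% power before attrition. It is therefore not shown to be wrong, and nothing below depends on it.

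**Assumptions.** Two-sided 5% tests, normal change scores, complete data, independent families, and a separate mean at each time point. The size of each test then has a closed form.

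**Formulas for n families.**

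- *Robust sandwich with z.* The sandwich variance of a mean change divides the sum of squared deviations by n², where the paired t test divides by n(n-1). The Wald z therefore equals the paired t times sqrt(n/(n-1)), and the size is P(|t(n-1)| > 1.960 × sqrt((n-1)/n)). For n = 18 the cut-off is 1.960 × sqrt(17/18) = 1.905 on 17 df. For n = 20 it is 1.960 × sqrt(19/20) = 1.910 on 19 df.
- *Uncorrected sandwich with t(n-1).* As above, with t(.975, n-1) in place of 1.960.
- *Model-based error with z, exchangeable correlation true.* P(|t(2(n-1))| > 1.960) with parameter-adjusted moment estimates. Without the adjustment the divisor is 3n in place of 3(n-1), and the cut-off becomes 1.960 × sqrt((n-1)/n).
- *Joint 2-df robust chi-square.* P(F(2, n-2) > 5.991(n-2)/(2n)). The cut-offs are 5.991 × 16/36 = 2.663 and 5.991 × 18/40 = 2.696.
- *Kauermann-Carroll with t(n-1).* Here the correction multiplies the variance by n/(n-1), which gives the paired t test.

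| Test | n = 18 | n = 20 |
|---|---|---|
| Robust sandwich, z | 7.4% | 7.1% |
| Uncorrected sandwich, t(n-1) | 5.6% | 5.6% |
| Model-based, z, adjusted moments | 5.8% | 5.7% |
| Model-based, z, unadjusted | 6.5% | 6.4% |
| Joint 2-df, robust chi-square | 10.0% | 9.5% |
| Kauermann-Carroll, t(n-1) | 5.0% | 5.0% |

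If the tests were one-sided, robust z would give 6.4% and 6.3%.

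**Consequences under robust z.** Interval coverage is 100 - 7.4 = 92.6% (n = 18) and 100 - 7.1 = 92.9% (n = 20). The uncorrected p that matches a calibrated .05 is 2 × (1 - Phi(t(.975, n-1) × sqrt(n/(n-1)))), which is .030 and .032. A robust-z p between those values and .05 would not fall below .05 in the corrected test. The corrected interval is wider by t(.975, n-1) / (1.960 × sqrt((n-1)/n)). This is 2.110/1.905 = 1.108 and 2.093/1.910 = 1.096.

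**Families without the last visit.** The complete-set rule admits them. In simulation (20 families, 2 or 4 without the final measure, exchangeable correlation .5, 20,000 trials each), robust z gave 7.1% and 7.6%, and Kauermann-Carroll with t(19) gave 4.9% and 5.2%. Counting all families in the fit as n is adequate for the 1-df test there.

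**Limits of the correction (simulated, assumed inputs).**

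- Skewed changes (gamma, shape 2): robust z 9.1% (n = 18) and 8.7% (n = 20) fall to 6.8% and 6.7%.
- Four leaders with five families each, and a leader intraclass correlation of .05 in change scores: about 9.9% falls to 7.3%. With .01, about 7.8% falls to 5.5%.

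**The case against.** The strongest reply is that the plan is silent, not wrong. It never names robust errors or z, and an analyst could use a corrected variance with a t reference and comply with every word. That stands, so each inflation figure is conditional on a choice still open. It does not remove the point, because GEE run in its usual form is too liberal at this number of families and nothing in the plan rules that out.

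A second reply is that the excess can be small. This also stands: the sandwich with a t reference gives 5.6%, and model-based errors with a correct working correlation give 5.7–6.5%.

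A reader might infer a larger small-sample problem from what happens when model-based errors use an exchangeable correlation and the truth is AR(1) with correlation .5. Simulated error is then 9.2–10.2% for baseline to the final measure and 4.2–4.8% for baseline to post-module 1. Most of that is a wrong working correlation and would remain with many families. The average correlation is (.5 + .5 + .25)/3 = .417, so the assumed variance of a change is 2(1 - .417) = 1.167. The true variances are 1.5 and 1.0, which gives large-sample errors of about 8.4% and 3.4%. The documents give no correlation structure, so this is not evidence about family numbers.

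Third, this is a convenience-sample pilot aimed at feasibility and acceptability. A pre/post p-value without a comparison group cannot establish an intervention effect, however well calibrated. Four outcomes with no multiplicity rule may matter more than two points of error. All of that stands and is why the point is minor.

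**Conclusion.** The point holds as a minor one. The plan applies GEE to 18–20 independent families at alpha .05 without a small-sample correction. If standard robust-z inference is used, a two-sided 1-df test of change has about 7.1–7.4% error and nominal 95% intervals cover about 92.6–92.9%. Milder uncorrected choices give about 5.6–6.5%, and a joint robust chi-square test of time about 9.5–10%. These sizes rest on normal changes, complete data, independent families and two-sided testing, none of which the plan states. The model-based figures also need a correct working correlation.

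A reader might infer that the trial will test at 7%, or that any uncorrected analysis is inflated by a fixed amount. The documents support neither: they do not choose an estimator or reference, and the size depends on that choice. Nor do they support saying that the correction secures 5%. Each Parent Leader serves several families ("Each Parent Leaders will be matched with approximately 4-5 caregivers each"), and leader clustering or marked skew would leave the corrected test above 5%. Conclusions on feasibility and acceptability do not depend on this.

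**What to change.** In Quantitative Data Analyses, add a sentence or two that:

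- names the primary time contrast for parenting stress and its sidedness;
- specifies GEE with time as a three-level factor, a bias-corrected sandwich variance (for example Kauermann-Carroll) and a t reference with n-1 df, where n is the number of families in the fit;
- if a joint test of time is reported, gives it a matching F reference. With W the Wald statistic on the corrected variance, refer (n-2)W/(2(n-1)) to F(2, n-2). This is exact only for complete, normal data, so it is approximate when final measures are missing.

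Kauermann-Carroll is not the only acceptable correction. A stronger bias-reduced sandwich with t(n-1) gives 4.4–4.5% in the same setting. What matters is to name one in advance.

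The cost is wording and a check that the chosen software offers the correction; no new data are needed. Intervals become about 11% (n = 18) or 10% (n = 20) wider than with uncorrected robust z. The change restores about 5% only for near-normal changes and independent families. Parent Leader clustering, multiplicity over four outcomes and the absence of a comparison group need separate statements.

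### On its natural reading, the complete-case rule drops every family without T1 data; the planned GEE on all observed waves would keep them at almost no cost

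*Combined protocol and SAP*

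**What the plan says.** All the analysis text is in the combined protocol and SAP, under Quantitative Data Analyses.

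- Model: "We will use Generalized Estimating Equations (GEE) to analyze changes over time in parenting stress, caregiver depression, child behavior, and family functioning". No analysis set is attached to this sentence.
- Analysis set: the next sentence introduces "complete case analysis, to validate intervention effects", and the one after it reads "In our study, we will consider baseline and T1 data (following completion of Module 1) a complete set".
- Missing data: measure manuals are followed for missing items and, where they give no guidance, "we will use the Markov chain Monte Carlo multiple imputation method to address item-level missing data". Nothing is said about a missing wave.
- Size: "we project a sample of 20 families adjusted for 10% attrition".

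Elsewhere, Design (Phase 3) states that "Intervention participants will complete measures at three time points", and Aim 2 states the target: "We will measure pre/post changes in child (challenging behaviors) and caregiver outcomes". Under Withdrawal of Participants, data collection stops once a family withdraws, so a family that withdraws before T1 has baseline data only. No section names an analysis of all available data, a sensitivity analysis, or a comparison of families with and without T1.

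**The concern.** A case counts as complete only with both baseline and T1, and whole waves are not imputed. Taken together, these rules exclude two kinds of family: those with baseline only, and those that missed T1 but returned after module 2. The second kind has an observed pre/post change that the rule discards.

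The reported change would then describe families with T1 data, while Aim 2 reads as a question about the enrolled families. T1 is collected after module 1 is completed, so a missing T1 may reflect early stopping. If early stopping is related to stress, the main outcome, the two groups may differ. If T1 is missing completely at random, only precision is lost.

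**Working it through.** **Inputs from the plan.** 20 families, 10% attrition, three waves (baseline, T1, T2 = post-module 2), complete set = baseline + T1.

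**The plan's own figure.** 18 / (1 − 0.10) = 20, so 20 is consistent with 18 evaluable families and a loss of 0.10 × 20 = 2. The power calculation behind it cannot be reproduced, because power, sidedness, effect-size metric and within-family correlation are not given. Nothing below depends on it.

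**How many families are affected.** The plan does not time the attrition. If all of it falls before T1, 2 of 20 families are dropped; if half does, 1 of 20.

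**Assumptions for size (none is in the documents).** Normal scores with SD 1; true change −0.15 SD at T1 and −0.30 SD at T2; common correlation r = .3, .5 or .7 between waves; 10% lost before T1 and also missing T2; log-odds of loss rising by 1 per SD of baseline stress. In a simulation of 1,000,000 families, those retained average about 0.09 SD below all enrolled at baseline.

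**Formula.** With working correlation ρ, the all-waves GEE gives

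T1 change = −0.15 − (r − ρ) × 0.09.

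Setting ρ = 0 gives independence GEE, and ρ = r gives correctly specified exchangeable GEE. The complete-case result equals the formula at ρ = 1, with bias (1 − r) × 0.09. T2 follows the same formula with −0.30 in place of −0.15.

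| r | complete-case bias | complete-case T1 / T2 | SE = √(2(1−r)/18) | bias / SE |
|---|---|---|---|---|
| .3 | 0.7 × 0.09 = 0.063 | −0.087 / −0.237 | 0.28 | 0.23 |
| .5 | 0.5 × 0.09 = 0.045 | −0.105 / −0.255 | 0.24 | 0.19 |
| .7 | 0.3 × 0.09 = 0.027 | −0.123 / −0.273 | 0.18 | 0.15 |

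The bias is toward less improvement in this scenario. With a slope of 0.5 it is about half as large.

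**GEE on all rows, r = .5.** Exchangeable: −0.15 and −0.30, so the bias is essentially gone. Independence: −0.15 − 0.5 × 0.09 = −0.195 and −0.345, a bias of similar size in the opposite direction. The working correlation therefore has to be stated.

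**A different mechanism.** If loss depends on poor change at T1 (10% loss, r = .5), complete case gives about −0.24 at T1 and −0.35 at T2. Keeping all waves gives about −0.22 and −0.32. The T1 bias falls only from 0.09 to 0.07 SD, so most of it stays. Here the bias flatters the program.

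**Total error in trials of 20 families.** With 10% loss, either random or depending on baseline, the all-waves analysis lowers root-mean-square error by about 1 to 3% when missed families have baseline only. The gain is about 6% at T2 if families that miss T1 still give T2 data. Uncorrected robust GEE intervals covered .91 to .93 instead of .95, so a small-sample correction is needed.

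**The case against.** The strongest reply is that the text does not clearly restrict the main analysis. The GEE sentence comes first and is unrestricted, and a complete-case analysis meant to validate effects can be read as a check on it. This stands as an alternative reading and lowers confidence. It does not remove the point, because no sentence says that the GEE uses all available data and the only case definition given is baseline plus T1.

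Three further objections also stand in part. The rule is already lenient: families lost during module 2 are kept, and that is not an error. Two of 20 is a ceiling under planned attrition. And a family with baseline only holds no direct information on its own change, so keeping it amounts to a baseline adjustment that depends on assumptions.

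A reader might go further and infer that the planned result is biased, or biased in favor of the program. The documents do not support that. They do not say why T1 would be missing, and the two mechanisms above move the estimate in opposite directions. A reader might also infer that GEE is the wrong model and should give way to a likelihood-based one. That does not follow: the sponsor's own GEE, run on all observed waves with an exchangeable correlation, removes essentially the same bias when loss depends on baseline.

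**Conclusion.** The point holds as a minor one, with moderate confidence because of the supporting-check reading. On the natural reading, families without T1 are dropped: at most 2 of 20 at the planned attrition, including any with baseline and post-module 2 data. Under assumed loss depending on baseline stress, complete-case bias is 0.03 to 0.06 SD, or 0.15 to 0.23 of a standard error. Those figures rest on the assumed slope, correlations and 10% loss before T1; they illustrate scale and are not estimates for this trial. In an uncontrolled pilot of 20 families the practical gain is small. It is worth taking because only wording changes and the analysis set becomes explicit under either reading.

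**What to change.** Keep the planned GEE and replace the complete-case rule with wording such as:

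> The primary analysis of each outcome will use GEE on every observed wave from every enrolled family, with time as a three-level factor, an exchangeable working correlation and a small-sample-corrected robust standard error. The analysis limited to families with baseline and T1 will be reported as a sensitivity analysis and labelled as change in families with T1 data. The number and baseline scores of families missing T1 or T2 will be tabulated.

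The item-level imputation rule can stay as it is. The choice of T1 or T2 as the main contrast remains with the sponsor.

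Cost: no extra families, surveys or payments. The analysis then relies on loss depending only on observed data and on the working correlation being roughly right. In the scenario above, an error of 0.2 in ρ would leave 0.2 × 0.09 = 0.018 SD of bias. The change helps little at T1 if poor early responders are the ones lost, and the table of missing families is the only guard the plan would have against overlooking that.
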